We will utilize connectome-based neurofeedback to assess patterns of functional connectivity within a previously identified “opioid abstinence network”. This network was identified using a whole-brain machine learning approach and predicted subsequent opioid relapse among methadone-maintained individuals. This network was robust, relatively unchanged in follow-up analyses controlling for other clinical variables (e.g., methadone dose, years of opioid use), predicted opioid relapse from different fMRI tasks as well as resting state, and predicted opioid use at multiple time points (two scanning sessions conducted 3 months apart). Design: Individuals on methadone (N=24) will receive active (n=24) connectome-based neurofeedback at 3 weekly scanning sessions (training scans 1-3). Training scans will include both feedback and transfer (i.e. no feedback) runs. Baseline (one week prior to training scan 1) and follow-up (one week following training scan 3) scans will be conducted to test the effects of feedback training on intrinsic connectivity during resting state and fMRI tasks, as in our pilot data. Clinical features of OUD (opioid use, craving, negative affect) will be assessed weekly and at one month follow-up.

Aim 1. To determine if connectome-based neurofeedback is associated with reduced opioid use. Aim 1a. We predict that individuals who receive active feedback will report lower

IRB# 2000025618

levels of opioid use from baseline to follow-up scans. *Aim 1b*. We predict that this reduction will persist over time as assessed at 1-month follow-up.

Aim 2. To determine if connectome-based neurofeedback is associated with changes in intrinsic connectivity. *Aim 2a*. Based on evidence that neurofeedback induces changes in intrinsic connectivity[13], we predict that subjects receiving active feedback will show increased opioid abstinence network connectivity during resting state at follow-up versus baseline scans. *Aim 2b*. We predict that this effect will generalize to increased connectivity during fMRI reward and cognitive tasks at these timepoints.

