Aim 3. To determine if connectome-based neurofeedback is associated with greater improvements in clinical features of opioid use disorder than sham feedback. *Aim 3a*. We predict that subjects who receive active feedback will show reduced craving and negative affect at follow-up versus baseline scans. *Aim 3b*. We predict that increased opioid abstinence network connectivity during transfer (no feedback) runs will be correlated with reduced craving and negative affect.

This proposal is significant by testing for the first time the effects of neurofeedback on large-scale network dynamics among individuals with opioid use disorder. This is a critical step toward understanding the neurobiology of opioid relapse and will pave the way for further treatment-oriented research.

2. **Probable Duration of Project:** State the expected duration of the project, including all follow-up and data analysis activities.

5 years

3. **Background:** Describe the background information that led to the plan for this project. Provide references to support the expectation of obtaining useful scientific data.

Write here

Need to understand brain functions in methadone treated individuals: Opioid use disorder (OUD) is a significant public health problem with opioid-associated overdoses and deaths rising significantly in recent years[14-16]. Methadone is a widely used and generally effective treatment for OUD, yet relapse rates remain high and treatment retention durations are suboptimal (e.g., <6 months in 30-50% of settings)[17-19]. As risk of overdose is highest following unsuccessful treatment (i.e., during a relapse)[20], improved mechanistic understanding of factors contributing to relapse in methadone patients is urgently needed to inform development of adjunct interventions to improve outcomes. We will leverage recent advances in connectome-based neurofeedback to probe large-scale patterns of brain functional connectivity previously linked to relapse among methadone-treated individuals with OUD. This is critical to improve our understanding of mechanisms contributing to relapse and an essential first step toward development of improved, evidence-based relapse prevention strategies.

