
4. **Research Plan:** Summarize the study design and research procedures using non-technical language that can be readily understood by someone outside the discipline. **Be sure to distinguish between standard of care vs. research procedures when applicable, and include any flowcharts of visits specifying their individual times and lengths.** Describe the setting in which the research will take place.

Study design: Participants will receive active ($n=24$) connectome-based feedback at three separate scanning sessions (training scans 1-3). . Training scans will include both neurofeedback and transfer (i.e., no feedback) runs conducted at weekly intervals (**Table 1**).

IRB# 2000025618

Additionally, to test the effects of feedback training on intrinsic

U-Tox	X	X	X	X
TLFB for substance use	X	X	X	X

connectivity, baseline (one week prior to training scan 1) and follow-up (one week following training scan 3) scans will be conducted and will include resting state and reward and cognitive task fMRI runs, to compare networks across brain states as in our prior work[49].

Screening visit: To determine eligibility subjects will first take part in a screening visit involving surveys about their health, smoking, substance use behaviors and attitudes, and the ways in which they view themselves. They will also complete a urine drug test. The screening session will take about 1 and ½ hours. If they are eligible, we will also schedule their MRI appointments during this visit.

Debriefing: At the end of the one month study visit, participants will be fully debriefed by study personnel, who will explain more thoroughly the purpose of the study and answer any questions they may have.

Opioid use: Opioid and other substance use will be monitored weekly at each MRI session from baseline to follow-up using urinalysis and the Timeline Followback (TLFB) [50] method, as in our prior work[10, 48]. Behavioral measures of clinical variables (e.g., pain, other substance use, craving and negative affect) will also be collected.

Imaging Protocol: Scanning will be conducted 2-3 hours following daily methadone on a 3T Siemens Prisma scanner with a 32-channel head coil. A member of the research staff will accompany each subject to the MRRC and stay with them for the duration of the study.

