for 10 seconds. We will use implicit feedback, in which subjects are kept unaware of the purpose of feedback, in order to more confidently attribute changes in behavior to modification of brain network dynamics by minimizing the use of explicit cognitive strategies and instead focusing on targeted neural processing[41]. This also avoids complicated instructions, reducing potential experimenter effects. Implicit feedback has been found to be robust and may be advantageous over explicit feedback[41]. The instructions will be, "Try methods that you have found to help you not use opioids or cope with craving in the past. The main thing is to try different strategies and see what works the best for you." Participants will be debriefed after each scan to ask whether they felt that they could control the feedback, and what strategies they used to try to control the feedback. This approach has been used previously including in our own work. [2-6] Transfer runs will be used to test control of the opioid abstinence network without feedback and will be exactly the same as feedback runs with the exception that a fixation cross will be displayed instead of the feedback bar. Subjects will be shown the same arrow cues and given the same instructions to increase the feedback bar.

Hypothesis testing: Network connectivity strength assessed at each scanning session will be entered into SPSS to test the following Specific Aims:

Aim 1: *To determine if connectome-based neurofeedback is associated with reduced opioid use compared with sham feedback.* H1a. Subjects receiving active versus sham feedback will report lower levels of opioid use from baseline to follow-up scans. H1b. This reduction will persist over time, as indicated by reduced opioid use through 1-mo follow-up.

Approach: Opioid use will be monitored by weekly urinalysis and TLFB across the five weeks from baseline to follow-up scans and measured as % negative urines (H1a); or will be measured using TLFB at 1-mo follow-up with abstinence at 1-mo confirmed by urinalysis (H1b). Medication compliance will be tracked via clinic records. Opioid use will be entered into a linear effects model with the between-subject factor of feedback group (active/sham).

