Aim 2: *To determine if connectome-based neurofeedback is associated with changes in intrinsic connectivity.* H2a. Subjects receiving active versus sham feedback will show increased opioid abstinence network connectivity between resting state acquired at follow-up versus baseline scans. H2b. This effect will generalize to increased connectivity during fMRI reward and cognitive tasks as in our pilot data.

Approach: Opioid abstinence network connectivity strength will be calculated during resting state (H2a), MIDT and Stroop tasks (H2b) as in our pilot data, and will be entered into a linear mixed effects model with the between-subject factor of feedback group (active/sham) and the within-subject factor of time (baseline/follow-up scans).

Aim 3: *To determine if connectome-based neurofeedback is associated with greater improvements in clinical features of OUD than sham feedback.* H3a. Subjects receiving active versus sham feedback will show reduced craving and negative affect at follow-up versus baseline scans. H3b. Increased opioid abstinence network connectivity during transfer runs will be correlated with reduced craving and negative affect.

Approach: Craving (Opioid Craving Scale) and negative affect (Quick Inventory of Depressive Symptomatology) will be calculated at follow-up and baseline scans and compared between groups using repeated measures analysis of variance. Change in opioid abstinence network connectivity strength will be calculated during transfer runs at baseline and follow-up scans. We will test for Pearson's correlations between change in connectivity strength and changes in craving and negative affect.

5. **Genetic Testing** N/A

6. **Subject Population:** Provide a detailed description of the types of human subjects who will be recruited into this study.

IRB# 2000025618

Write here

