This protocol presents minimal risks to the subjects and Unanticipated Problems Involving Risks to Subjects or Others (UPIRSOs), including adverse events, are not anticipated. In the unlikely event that such events occur, Reportable Events (which are events that are serious or life-threatening and unanticipated (or anticipated but occurring with a greater frequency than expected) and possibly, probably, or definitely related) or Unanticipated Problems Involving Risks to Subjects or Others that may require a temporary or permanent interruption of study activities will be reported immediately (if possible), followed by a written report within 5 calendar days of the Principal Investigators becoming aware of the event to the IRB (using the appropriate forms from the website) and any appropriate funding and regulatory agencies. The investigators will apprise fellow investigators and study personnel of all UPIRSOs and adverse events that occur during the conduct of this research project through regular study emails or via email as they are reviewed by the principal investigators. The protocol's research monitor(s), study sponsors, funding and regulatory agencies, and regulatory and decision-making bodies will be informed of serious and unanticipated and related adverse events or unanticipated problems involving risks to subjects or others will be reported adverse events within 5 days of the event becoming known to the principal investigator.

13. Statistical Considerations: Describe the statistical analyses that support the study design.

Write here

Our previous neurofeedback work showed that data from 10-20 subjects is adequate for demonstrating significant control of activity in a single brain region[13, 65, 68, 69] and that data from two groups of 10-20 subjects is adequate for detecting group differences in control of activity[13, 68]. Our prior CPM work showed that data from N=10 per group is sufficiently powered

IRB# 2000025618

(>.90) to detect differences in connectome-based networks (noncentrality parameter (δ)=5.36, critical t-value=2.10, df=18, power (1- β)=0.99). Finally, we have established retention rates of >85% over 3-months for fMRI studies with methadone patients[10, 70]. Thus, we are confident that a sample size of N=24 (N=12 per group) is sufficiently powered.

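### The stated design gives all 24 participants active feedback, but the tests and power statement compare active with sham, so no group effect is estimable and Aim 1 has no usable test

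*Combined protocol and SAP*

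**What the plan says.** **Design.** Section I.1 states: "Individuals on methadone (N=24) will receive active (n=24) connectome-based neurofeedback at 3 weekly scanning sessions (training scans 1-3"). The study design paragraph of Section I.4 again puts n=24 on active feedback, describing "connectome-based feedback at three separate scanning sessions (training scans 1-3"). Neither place, nor any other, describes a sham signal, a sham sample size, randomisation or allocation.

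**Aims in Section I.1.** Aims 1, 2 and 3a are worded as change within people who receive active feedback. Aim 3a, for example, reads: "We predict that subjects who receive active feedback will show reduced craving and negative affect at follow-up versus baseline scans". Only the heading of Aim 3 still mentions sham.

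**Hypotheses and models in Sections I.4 and I.13.** H1a, H2a and H3a are worded as active versus sham.
- Aim 1 (both sections): "Opioid use will be entered into a linear effects model with the between-subject factor of feedback group (active/sham"). No other factor is named. The H1a outcome is percent negative urines over the five weeks from baseline to follow-up. H1b uses TLFB at one month, with abstinence confirmed by urinalysis.
- Aim 2: connectivity strength "will be entered into a linear mixed effects model with the between-subject factor of feedback group (active/sham) and the within-subject factor of time".
- Aim 3a: craving and negative affect are "compared between groups using repeated measures analysis of variance" in Section I.4, and analysed by a mixed model with group and time in Section I.13.

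**Sample size.** Section I.13 concludes: "Thus, we are confident that a sample size of N=24 (N=12 per group) is sufficiently powered".

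**Payments.** Section VI.2 says, in the past tense, that some participants received sham feedback. It gives no number and no role in the analysis.

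**The concern.** The design and the analysis describe different trials. If the design sections are right, the group factor is constant and every contrast built on it disappears.

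- **Aim 1** cannot be tested as written, for H1a or H1b. An analyst would have to devise the opioid-use test after the data exist.
- **Aims 2 and 3a** keep a time effect, but Section I.4 words H2a and H3a as comparisons with sham. A before-and-after change could be reported under a sham-controlled hypothesis.
- **The sample size** is supported by a comparison that the stated design does not contain.
- **The payments text** leaves open whether people given sham feedback are among the 24, and whether their data enter any analysis.

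**Working it through.** **1. The plan's own power figure**

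Inputs (Section I.13): noncentrality 5.36, critical t 2.10, df 18, 10 per group, power 0.99.

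- Alpha is not stated. The two-sided 0.05 critical value is t(0.975, 18) = 2.101, which matches 2.10. The one-sided value would be 1.734. Two-sided 0.05 is therefore inferred.
- Power from the noncentral t distribution (df 18, noncentrality 5.36) is 0.999, in line with the stated 0.99.
- Implied effect: d = 5.36 / √(10 × 10 / 20) = 5.36 / 2.236 = 2.40, a difference between two independent groups.

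The arithmetic is sound, but it applies to a two-group contrast.

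**2. What the models can estimate when all 24 are active**

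| Model | Columns | Rank | Estimable |
|---|---|---|---|
| Aim 1 | intercept, group | 1 of 2 | overall mean only |
| Aims 2 and 3a, 24 people × 2 visits | intercept, group, time, group × time | 2 of 4 | intercept and time |

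Group equals 1 for everyone, so it duplicates the intercept, and group × time duplicates time.

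**3. Whether Aim 1 can be rescued by dropping group**

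- H1a: dropping group leaves only an intercept. Percent negative urines is one summary per person. Its period starts at the baseline scan, where Table 1 schedules a urine test, so it is read here as including the baseline urine. There is no separate baseline value to compare it with.
- H1b: TLFB does have a baseline counterpart in Table 1, but the model has no time factor and no contrast is named.

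H3b and the replication correlation need no group factor and are unaffected.

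**4. What 24 pairs can detect**

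One-sample noncentral t on change scores, n = 24, df = 23, two-sided 0.05, noncentrality dz × √24, where dz is the mean change divided by the SD of change:

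- 80% power at dz = 0.597
- 90% power at dz = 0.691
- 95% CI half-width = t(0.975, 23) / √24 = 2.069 / 4.899 = 0.422 SD of change

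In single-visit SD units the effect is dz × √(2(1 − r)). The baseline to follow-up correlation r is not in the documents, so a range is assumed:

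| Assumed r | Effect at 80% power (single-visit SDs) |
|---|---|
| 0.3 | 0.597 × √1.4 = 0.71 |
| 0.5 | 0.597 × √1.0 = 0.60 |
| 0.7 | 0.597 × √0.6 = 0.46 |

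A dz is not on the same scale as the two-group d of 2.40. None of these figures applies to percent negative urines, which has no paired baseline value.

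**The case against.** The strongest reply is that the protocol does not settle on one arm. The payments text refers to sham recipients, the sample-size statement has two groups of 12, and the description of the feedback runs in Section I.4 speaks of an active feedback group. If some sham participants entered the analysis, the Aim 2 and 3a matrix would regain full rank; adding four, for instance, gives 4 of 4. This stands as a limit: the rank results hold for the design as stated in Sections I.1 and I.4. It does not rescue the plan, which gives no sham number, allocation or analysis role.

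The harm to Aims 2 and 3a is also limited. Section I.1 words them as follow-up versus baseline, so the surviving time effect does test the aims as stated there. For these aims the repair is to remove a factor and align the wording of Section I.4.

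Section I.13 also cites 10 to 20 subjects as adequate in earlier work. The single-group part of that statement concerns control of one brain region, not opioid use, network connectivity, craving or affect, so it does not size these endpoints.

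Two cautions apply to the paired figures. The documents give no SD or expected change, so dz = 0.60 is a sensitivity figure, not evidence of adequacy. It also needs 24 complete pairs. Section III.1 targets 24 completers, but Section I.6 plans to enrol 24. At its quoted 86% retention, 24 × 0.86 = 20.6, or about 21 pairs, and 80% power would then need dz = 0.64.

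Finally, moving H1a to TLFB puts more weight on self-report. A visit-level model of the weekly urines over time is a possible alternative that keeps the protocol's measure.

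**Conclusion.** The concern holds and must be fixed. Under the stated design of 24 active participants, no group or group-by-time effect can be estimated in any aim, and Aim 1 has no pre-specified test. Aims 2 and 3a retain a valid time effect, but it is not the hypothesis written in Section I.4. The power statement reproduces, but for a two-group d of 2.40 that has no counterpart in a one-arm study.

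The estimability result rests on Sections I.1 and I.4 being the intended design. The replacement power figures rest on two-sided 0.05 (inferred from the critical t), 24 complete pairs and an approximately normal change score.

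**What to change.** Amend Sections I.4 and I.13, with matching edits elsewhere:

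1. Reword H1a, H2a, H3a and the Aim 1 and Aim 3 headings as within-person change, consistent with the aims in Section I.1. The Aim 3 heading in Section I.1 needs the same edit.
2. For H2a, H2b and H3a, use a linear mixed model with time (baseline, follow-up) and a participant random intercept. Report the time coefficient with its 95% CI.
3. For Aim 1, name a within-person contrast on a measure taken before and after training. One option is opioid-use days from "TLFB for substance use" in equal, pre-stated look-back windows: baseline versus follow-up scan for H1a, and baseline versus one month for H1b, with visit-level urine results as support. The follow-up scan is one week after training scan 3, so a window longer than about a week would overlap training. The choice of window should address this.
4. Replace the 12-per-group statement with one for the paired design (n=24: dz 0.60 at 80% power, 0.69 at 90%), stating its assumptions and the number of complete pairs expected.
5. State that the result is an uncontrolled change. It cannot separate feedback from time, repeated assessment or practice of coping strategies. For opioid use it also cannot exclude regression to the mean, since recent use is an entry criterion.
6. Reconcile Section VI.2. Say whether anyone received sham, how many, whether they are among the 24 completers or the up to 40 people scanned (Section III.2), and whether their data enter any analysis. If a sham arm is still intended, correct the design text in Sections I.1 and I.4 instead, and give the allocation method and the sample size per arm.

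**Cost.** A protocol amendment that changes the hypotheses, the Aim 1 estimand and the sample-size rationale. Under the one-arm route no visits, measures or patients are added, because Table 1 already schedules TLFB and urine toxicology at baseline, training, follow-up and one month. The sponsor gives up a sham-controlled claim that the one-arm design cannot support.

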The statistical tests will be as follows: Aim 1: Opioid use will be entered into a linear effects model with the between-subject factor of feedback group (active/sham). Aim 2: Opioid abstinence network strength during resting state and task fMRI runs will be compared between time points using linear mixed models with the between-subject factor of group (active/sham) and the within-subject factor of time (baseline/follow-up scan). Aim 3: Craving and negative affect will be compared using linear mixed effects model with the between-subject factor of group (active/sham) and the within-subject factor of time (baseline/follow-up scan). Associations between craving and negative affect and opioid abstinence network connectivity strength during transfer runs will be tested using Pearson's or Spearman's correlations, as appropriate depending on the distribution of the data. Replication: For replication of our pilot data (Figure 2 of research strategy), Pearson's correlations will be tested between opioid abstinence network connectivity strength at baseline and percent opioid-negative urines across the study.

SECTION II: RESEARCH INVOLVING DRUGS, BIOLOGICS, RADIOTRACERS, PLACEBOS AND DEVICES

If this section (or one of its parts, A or B) is not applicable, check off N/A and delete the rest of the section.

A. RADIOTRACERS N/A

B. DRUGS/BIOLOGICS N/A

C. DEVICES N/A

SECTION III: RECRUITMENT/CONSENT AND ASSENT PROCEDURES

1. Targeted Enrollment: Give the number of subjects:

- a. Targeted for enrollment at Yale for this protocol:
24 completers (individuals participating in all scanning sessions).
- b. If this is a multi-site study, give the total number of subjects targeted across all sites: NA

2. Indicate recruitment methods below. Attach copies of any recruitment materials that will be used.

 Flyers	 Internet/web postings	 Radio
 Posters	 Mass email solicitation	 Telephone
 Letter	 Departmental/Center website	 Television
 Medical record review*	 Departmental/Center research boards	 Newspaper
 Departmental/Center newsletters	 Web-based clinical trial registries	 Clinicaltrials.gov

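### Aim 1 predicts a fall in opioid use from baseline, but its only model is an active/sham factor with no time term: untestable if the trial is single-arm, incomplete if a sham arm is kept

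*Combined protocol and SAP*

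**What the plan says.** **Prediction.** Section I, 1 (Statement of Purpose), Aim 1a predicts lower opioid use from baseline to follow-up in people given active feedback. Aim 1b adds: "We predict that this reduction will persist over time as assessed at 1-month follow-up". Section I, 4 (Hypothesis testing) restates these as a comparison with sham. H1a is "Subjects receiving active versus sham feedback will report lower levels of opioid use from baseline to follow-up scans", and H1b is "This reduction will persist over time, as indicated by reduced opioid use through 1-mo follow-up".

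**Measures.** For H1a, use is monitored "across the five weeks from baseline to follow-up scans and measured as % negative urines (H1a"). The sentence goes on, "or will be measured using TLFB at 1-mo follow-up with abstinence at 1-mo confirmed by urinalysis (H1b").

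**Model.** Hypothesis testing gives "Opioid use will be entered into a linear effects model with the between-subject factor of feedback group (active/sham"). Section I, 13 (Statistical Considerations) repeats it: "Aim 1: Opioid use will be entered into a linear effects model with the between-subject factor of feedback group (active/sham"). For Aims 2 and 3, Section I, 13 adds a within-subject factor of time (baseline and follow-up scan).

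**Design.** The Statement of Purpose says: "Individuals on methadone (N=24) will receive active (n=24) connectome-based neurofeedback at 3 weekly scanning sessions". The Study design paragraph of Section I, 4 agrees. A sham or second group still appears in five places:
- Aim 3 of the Statement of Purpose;
- the paragraph on neurofeedback and transfer runs, by implication;
- Hypothesis testing;
- the sample-size text and tests in Section I, 13 (12 per group);
- Section VI, 2 (Payments), in the past tense.

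**Data.** Table 1 schedules urine toxicology and TLFB at baseline, training 1-3, follow-up and 1 month. No TLFB look-back period is given.

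**The concern.** A reduction that persists is a change from baseline, yet the Aim 1 model contains nothing that refers to baseline. The consequence depends on which design is in force.

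If all 24 receive active feedback, the only term in the model cannot be estimated. Aims 2 and 3 could drop the group factor and still compare baseline with follow-up. Aim 1 would have nothing left to test, so the analysis of the clinical outcome would have to be chosen after the fact.

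If a sham arm exists, the stakes are lower: dilution of the group difference by pre-feedback urines, and an H1b with no stated starting point from which a reduction could persist.

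**Working it through.** **1. The plan's own power figure.** Section I, 13 gives noncentrality 5.36, critical t 2.10, df 18 and power 0.99. Taking two-sided alpha as 0.05 (not stated), the critical t is 2.101 and the noncentral-t power is 0.999, so the figure reproduces. It implies d = 5.36 / sqrt(10 x 10 / 20) = 2.40 for a difference in connectome networks. No power figure is given for opioid use, so it does not bear on Aim 1.

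**2. Can the model be fitted with 24 active and 0 sham?** The design matrix has an intercept column of 24 ones and a group column of 24 ones. Its rank is 1, so the group effect is not estimable. Without the group column only the mean level of use remains.

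**3. Can the H1a percentage stand in for change?** Visits are weekly, at days 0, 7, 14, 21 and 28. Assuming one urine per visit, there are 5 urines and 2^5 = 32 possible sequences. Ten sequences score 3/5 = 60% negative. From first to last urine, 3 of these improve, 4 do not change and 3 worsen. The 10 sequences at 2/5 = 40% split the same way. At these scores the pooled percentage does not say whether use fell.

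**4. Dilution if a sham arm exists.** No sentence defines the denominator; the natural reading includes the baseline urine.
- Baseline urine only before feedback: 4/5 = 0.80 of the difference remains, so 20 points appear as 16.
- Training-1 sample also precedes feedback: 3/5 = 0.60 remains, so 20 points appear as 12.

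**5. Precision of a baseline-referenced analysis** (two-sided 5% assumed; 24 completers, from Section III, 1).
- Paired t, n = 24: 80% power at a mean change of 0.597 SD of the change score. The 95% CI half-width is t(23) / sqrt(24) = 2.069 / 4.899 = 0.422 SD.
- In SD of the level, multiply by sqrt(2(1 - r)): 0.71 at an assumed baseline/follow-up correlation r = 0.3, and 0.46 at r = 0.7.
- 12 per arm: 1.20 SD unadjusted; about 1.14 to 0.86 SD adjusted for baseline at r = 0.3 to 0.7.

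**6. Power of a urine-only pre/post comparison.** This was simulated with a paired t on period means for 24 complete participants. The assumptions are baseline negative rates of 20% to 60%, a logit random-intercept SD of 0.5 to 2.5, and a gain that starts after the training-1 urine. The limits are approximate, to about 0.02.

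| Split (pre v post) | 10 points | 20 points | 30 points |
|---|---|---|---|
| 1 v 4 (training-1 urine counted as post) | 0.09-0.19 | 0.23-0.49 | 0.51-0.80 |
| 2 v 3 (training-1 urine counted as pre) | 0.19-0.36 | 0.57-0.85 | 0.90-0.99 |

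**The case against.** The strongest reply is that the single-level factor belongs to the unresolved design conflict, which touches every aim, and is not a fault of the Aim 1 model. With a randomised sham arm, a group comparison of percent negative urines over a period is a legitimate analysis. H1a can be read as exactly that, and the team used the same kind of period outcome in the cocaine work described under Background. Aims 2 and 3 use point measures, so their time factor sets no rule for a period summary.

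Most of this stands. A reader might infer that the Aim 1 model is wrong under either design; the documents do not support that. What survives is that resolving the conflict in favour of the single-arm text rescues Aims 2 and 3 but leaves Aim 1 without a test.

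A second reply concerns the measures. Urine and TLFB are both collected in both periods, and one urine at 1 month cannot give an informative percentage, so a change of emphasis for H1b is understandable. That also stands. A reader might infer that H1a and H1b rest on unrelated instruments, or that TLFB has to become the primary measure. The first overstates a missing contrast, and the second is a preference.

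**Conclusion.** The point holds, with a severity that depends on the design.

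- **Single-arm:** Aim 1 cannot be tested as written and must be fixed. This follows from the model terms and the allocation alone and needs no assumed figure.
- **Sham arm retained:** the group comparison is valid. The percentage probably includes one or two pre-feedback urines (dilution to 80% or 60%, assuming five urines and a constant later difference), and H1b lacks a baseline contrast. This should be fixed.

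The change reading rests on Aims 1a and 1b and on the word reduction in H1b; H1a in Hypothesis testing, taken alone, could mean a level. A reader might also infer that the data for a change analysis are missing. They are not: Table 1 schedules both measures at baseline, follow-up and 1 month, so the gap is in the analysis text. The precision and power figures are illustrations on stated assumptions, because the documents give no SD, effect size or correlation for opioid use.

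**What to change.** 1. Reconcile the single-arm and sham passages, and state who enters the Aim 1 analysis.
2. **If single-arm**, replace the Aim 1 model with a within-person time model that uses the baseline visit as reference: baseline v follow-up (or post-training) for H1a, and baseline v 1 month for H1b. Use the same measure at every time point within a hypothesis. Report an association, not an effect of feedback.
3. **If a sham arm is retained**, add group-by-time terms or adjust post-training use for baseline, and leave pre-feedback urines out of the outcome percentage.
4. H1a can stay on urine through visit-level results, pre- v post-training, with the training-1 urine assigned in advance to the pre-training period. TLFB may run alongside for both hypotheses with its look-back stated.
5. If TLFB is used, choose a baseline window that exists in the data and does not reach back before screening. If screening were one week before baseline (assumed), a 21-day window would include 21 - 7 = 14 days before screening. A weekly window is the safest.
6. Warn that an uncontrolled change may partly be regression to the mean, because entry requires recent opioid use (Section I, 6 and 8).

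The cost is analysis wording on assessments already scheduled, provided the TLFB window chosen was actually recorded. The downsides are the limited precision shown above and that TLFB is self-report. The past tense in Section VI, 2 suggests that some participants may already have been treated. If outcomes have been seen, the revised analysis must be labelled as not prespecified.
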